Methodology	
Subjects enrolled into the study will be transferred from the selected company-sponsored feeder trials with radium-223 dichloride. Subjects, their treating health care professional, or caregiver will be contacted by telephone (face-to-face data collection is possible and will replace the telephone contact if the subject is on-site within the time window of the planned telephone contact) every 6 months (<math>\pm</math> 28 days) for 7 years (or as defined in the feeder trial protocols) following the last dose of radium-223 dichloride or placebo in the feeder trial, or until death, to determine the following:
 
 
• All radium-223 dichloride-/placebo-related adverse events (AEs) and serious adverse events (SAEs)
 
• All occurrences of leukemia, myelodysplastic syndrome, aplastic anemia, and primary bone cancer or any other new primary malignancy
 
• All bone fractures and bone associated events (e.g., osteoporosis) should be collected as either AEs or SAEs if the criteria of SAE were met, regardless of the investigator's causality assessment.
 
• Cancer treatment (including any systemic cytotoxic chemotherapy or radiotherapy for any malignancy; androgen synthesis inhibitors / androgen-receptor antagonists and radiation treatment; excluding analgesics)
 
• In subjects who receive cytotoxic chemotherapy: all occurrences of febrile neutropenia or hemorrhage during their chemotherapy treatment and for up to 6 months thereafter
 
• Survival status.
 
 
Subject data collected at other standard-of-care visits and / or contacts may be used to satisfy study-required data.
 
Section modified by Amendments 1 and 2.

Type of control	Not applicable
Number of subjects	With the currently active feeder trials, approximately 800 subjects are expected to be enrolled into this long-term safety follow-up study, but the number of subjects may increase if additional trials feed into this study.

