The key attribute of radium-223 dichloride is its specific targeting of bone with limited radiation exposure beyond the intended target. However, the proximity of the bone marrow space to site of action of radium-223 dichloride means that there is potential for radiationinduced bone marrow abnormalities. These abnormalities, including bone marrow dysplasia or new primary malignancies, may not become evident until years after the initial exposure to radium-223 dichloride; therefore, longterm follow-up is required to detect them. The ERA 223 study, a phase III randomized trial in prostate cancer participants examining radium-223 dichloride versus placebo in combination with abiraterone and prednisone (study number 15396, NCT02043678) was unblinded based on the Independent Data Monitoring Committee (IDMC) recommendation following an ad hoc independent analysis where more treatmentemergent fractures and total deaths were observed in the active treatment arm compared with the placebo arm. The IDMC also recommended that all bone fractures and bone-associated events (e.g., osteoporosis) occurring in follow-up period are to be documented regardless of investigator's causality assessment. In order to collect comprehensive safety information across all clinical trials with radium-223 dichloride, documentation of fractures (pathological and non-pathological) regardless of relationship, is also implemented in the present trial. In addition, any bone health agent taken during the study period is being collected.

The follow-up period in this study extends to up to 7 years after the last dose of radium-223 dichloride or placebo.

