5.1 General Principles

Long-term follow-up data may have been collected within the feeder study, within study 16996, or both. However, only follow-up data (e.g. adverse event data and anti-cancer medication/therapy data) that are collected during study 16996 will be included in the analyses described in this SAP. Limited information from feeder studies will be integrated with study 16996 (Section 5.2.1) to provide summaries of treatment exposure, overall follow-up duration and baseline characteristics at entry into feeder study. As noted in Section 7.2 below, this reduced analysis represents a deviation from the protocol-planned analysis.

Except if otherwise specified, participants will be included in the analyses according to the treatment they received in their feeder trial. Summaries will be presented by indication, feeder study and treatment arm within the feeder study. Listings will be produced by feeder trial arm containing participant data from study 16996, based on the ENR or SAF-LTF set, as applicable.

No formal statistical testing is planned for the overall analysis. The statistical evaluation will be performed by using the software package SAS release 9.4 or higher (SAS Institute Inc., Cary, NC, USA). Data will be analyzed using descriptive statistical methods.

Unless otherwise specified, the following descriptive statistics will be presented in data summaries:

- For continuous or ordinal data, the number of participants with data available (n), arithmetic mean, standard deviation (SD), minimum (min), quartile, median, maximum (max) will be presented.
- For categorical variables, the number of participants and percentage in each category will be presented.

The structure of analysis datasets and layout of analyses and data displays will follow Bayer AG standards, including Therapeutic Area Oncology Standards (TAS) and the Global Medical Standards (GMS), as applicable.

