5.2 Data rules

5.2.1 Integrating Feeder Study Data

Information to be integrated from feeder studies will include (if available): unique participant identifiers (ID), demographic and baseline characteristics (age, height, and weight), intervention randomized to, intervention received, and treatment exposure data, including date of first administration of study drug, date of last radium-223 dichloride or placebo and number of injections received. Only data from eligible feeder studies will be integrated. Data will be merged by feeder study unique subject ID as documented in the 16996 CRF.

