5.3 Handling of Dropouts

A participant who discontinues study participation prematurely for any reason is defined as a "drop-out".

Premature discontinuation from study 16996 is defined as discontinuation from study 16996 prior to the end of the applicable long-term-follow-up period from the last date of radium-223 dichloride or placebo treatment in the feeder study (5 years for mBC, 7 years for mCRPC).

The reason for discontinuation for participants who withdraw from study 16996 will be recorded in the electronic case report form (eCRF) and summarized in the analysis. Summaries of premature discontinuation will be provided for SAF-LTF participants.

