6.1 Population Characteristics

6.1.1 Participant Disposition

The number and percentage of ENR participants valid for SAF-LTF will be presented by treatment group, for the overall total of the treatment groups per feeder study, and pooled for the total of Study 16996.

The number of participants enrolled in 16996 (ENR) will be displayed by geographic region, country/region and center for each feeder trial.

Protocol No.: **BAY 88-8223/16996** Page: 10 of 17

Study disposition including the number and percent of participants who enrolled in 16996, who did not complete screening, who entered 16996 long-term follow-up, who discontinued long-term follow-up, and who completed long-term follow-up will be summarized for ENR participants. Reasons for premature withdrawal from long-term follow-up will be provided. Summaries will be provided overall (pooled across feeder studies), by feeder study, and by treatment group within each feeder study.

In addition, summary statistics for the duration of follow-up in SAF-LTF participants, period from 31 days (inclusive) after the last administration of radium-223 dichloride or placebo in the feeder study until the last known alive date, will be presented, and the numbers of participants with at least 6, 12, 18, 24, 36, 48, 60, 72, and 84 months of follow-up will be summarized. This summary of long-term follow-up analysis will combine feeder study and 16996 data.

Summary statistics for the duration of follow-up in study 16996 from the time of signing of the informed consent until the last known alive date in SAF-LTF participants will also be presented. The numbers of participants with at least 6, 12, 18, 24, 36, 48, 60, 72, and 84 months of follow-up will be summarized.

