Per protocol, febrile neutropenia and hemorrhage AEs are to be collected during and within 6 months of cytotoxic chemotherapy treatment. For the protocol-specified analysis of the incidence of febrile neutropenia or hemorrhage during their chemotherapy treatment and for up to 6 months thereafter, a simplified analysis will be performed, of febrile neutropenia and hemorrhage AEs without regard to cytotoxic chemotherapy association. All 16996-emergent febrile neutropenia and hemorrhage AEs documented in the study CRF will be reported, without regard to chemotherapy treatment.

For the analysis of fractures and bone associated events, separate analyses of patients with bone fractures, patients with bone associated events, and patients with bone fractures and/or bone associated events will be performed. The applicable MedDRA appendix will identify the MedDRA preferred terms applicable to each sub-category.

Unless otherwise specified, the analysis for each AE category will include a summary of the total number and percent of SAF-LTF participants with an AE of the applicable category. Participants with an applicable AE will be summarized by MedDRA preferred term (PT), overall within each applicable MedDRA system organ class (SOC), and overall (any applicable AE), both by worst CTCAE grade and for any grade. For summaries by worst grade, the AE with the worst grade in the applicable summary category will be used. AEs with missing grade will be included in any-grade summaries but not in summaries by worst grade. In addition, listings will be provided.

6.4.2.1 16996-Collected Adverse Events

All AEs collected in study 16996, whether or not collection was required per study 16996 protocol, will be listed for SAF-LTF including AE PT, 16996-emergent (Y/N), start and stop dates, grade, treatment-related (Y/N), serious (Y/N), reason for seriousness, outcome of AE, and time (days) since last dose of study drug. The listing will include all 16996-collected AEs, whether or not emerging within study 16996.

6.4.2.2 16996-Emergent Adverse Events

Summaries of the total number and percent of SAF-LTF participants with an AE of the following categories of 16996-emergent AEs will be presented:

• All 16996-emergent adverse events

Statistical Analysis Plan

Protocol No.: BAY 88-8223/16996

Page: 13 of 17

- Radium-223 dichloride- or placebo-related 16996-emergent AEs;
- Radium-223 dichloride- or placebo-related serious 16996-emergent AEs;

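### This SAP breaks no primary event summary down by time since last dose, so its percents cannot tell a late rise in risk from a constant rate

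*SAP*

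**What the plan says.** **Purpose.** SAP 1, like Protocol 1.2, rests the follow-up on latency: "These abnormalities, including bone marrow dysplasia or new primary malignancies, may not become evident until years after the initial exposure to radium-223 dichloride". Follow-up after the last dose depends on indication ("5 years for mBC, 7 years for mCRPC", SAP 5.3).

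**Event summaries.** Under SAP 6.4.2 each category receives "a summary of the total number and percent of SAF-LTF participants with an AE of the applicable category", in line with the general default in SAP 5.1 ("For categorical variables, the number of participants and percentage in each category will be presented"). Tables are split by preferred term, system organ class and worst grade, and by indication, feeder study and arm. None is split by time. Only events arising or worsening after consent to 16996 are counted in these tables.

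**Measures removed.** Protocol 8.3.2.1 lists incidence proportion, incidence rate and cumulative incidence as possible measures, and names length of follow-up and time-to-event methods as considerations. The document history in SAP 7.1 records that version 2 took out incidence rates and cumulative incidence. SAP 7.2, which lists departures from the protocol's planned analyses, does not mention this.

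**Where time does appear.**
- The adverse event listing in SAP 6.4.2.1 gives days since last dose for each collected event.
- SAP 6.1.1 plans two follow-up tables. One runs from 31 days after last dose ("This summary of long-term follow-up analysis will combine feeder study and 16996 data"); the other runs from 16996 consent.
- SAP 5.5 places separate analyses per feeder study in a supplemental SAP for Health Authority reports, which is not among the documents.

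**The concern.** The study asks whether risk changes with time since exposure. A percent over the whole counted period has no time axis, so the same value can come from a steady background rate or from a low rate that climbs late. A reader of the final tables could not tell which had occurred. At stake is the interpretation of new primary malignancies and marrow disease in a study run partly to meet an FDA post-marketing requirement (Protocol 1.2).

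This is a separate matter from unequal follow-up between arms. One overall person-time rate would correct for unequal follow-up and still not show a late rise.

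**Working it through.** The plan gives no sample size calculation, power or event rate, so there is no figure of its own to reproduce. Three checks follow.

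**1. Do the other outputs supply a matching denominator?**

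| Output | What it gives | What is missing |
|---|---|---|
| AE listing, SAP 6.4.2.1 | Days since last dose, per event | Cases only, no time at risk |
| Follow-up from day 31 after last dose, SAP 6.1.1 | Dose-based time scale | Includes time before consent, when no event can be 16996-emergent |
| Follow-up from consent, SAP 6.1.1 | The period in which events count | Not on the time-since-dose scale |

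None of the three gives person-time that is both on the dose scale and confined to the counted period.

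**2. Can the percent separate the two patterns?** Assume everyone is followed from last dose to year 7, with a constant death hazard μ = ln 2 / median survival and event rate h1 up to year 4, then h2. The proportion with an event is

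h1·(1 − e^(−4(h1+μ)))/(h1+μ) + e^(−4(h1+μ))·h2·(1 − e^(−3(h2+μ)))/(h2+μ).

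For the median I use 28 and 36 months, the survival range that Protocol 1.1 gives for metastatic prostate cancer on initial androgen deprivation. It serves as illustration only. The event rates and the cut at year 4 are assumptions.

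- Median 28 months: a flat 5 per 1000 person-years gives 1.46%. A rate of 2.46 rising to 15 per 1000 also gives 1.46%.
- Median 36 months: a flat 5 per 1000 gives 1.71%. A rate of 1.76 rising to 15 per 1000 also gives 1.71%.

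**3. How much would a late rise move the percent?** N = 800 comes from the Protocol Synopsis ("approximately 800 subjects are expected to be enrolled into this long-term safety follow-up study"). The rest is assumed: entry at e = 0.5 or 1 year after last dose, exponential survival from entry with median 1.5 to 4 years, background 1 event per 100 person-years, and everyone observable to year 7. With λ = ln 2 / median,

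person-years from a to b = N·[e^(−λ(a−e)) − e^(−λ(b−e))]/λ.

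Events are rate × person-years. Tripling the rate in an interval multiplies the total by 1 + 2 × (that interval's share of person-time).

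Example, e = 1 and median 2 years: λ = 0.3466 and N/λ = 2308.
- Years 1–2: 2308 × (1 − 0.7071) = 676
- Years 2–5: 2308 × (0.7071 − 0.25) = 1055
- Years 5–7: 2308 × (0.25 − 0.125) = 289
- Background: 20.2 events, 2.52%; standard error √(0.0252 × 0.9748/800) = 0.55 percentage points
- Tripled in years 5–7 only: 20.2 + 2 × 2.89 = 26.0 events, 3.25%, a shift of 1.3 standard errors
- Tripled from year 2: 20.2 + 2 × 13.4 = 47.1 events, 5.9%, a shift of about 6 standard errors

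| Entry (y) | Median (y) | Share in years 5–7 | Factor, tripled in years 5–7 | Share after year 2 | Factor, tripled from year 2 |
|---|---|---|---|---|---|
| 0.5 | 1.5 | 7.9% | 1.16 | 47% | 1.95 |
| 0.5 | 2 | 11.7% | 1.23 | 55% | 2.09 |
| 0.5 | 3 | 16.8% | 1.34 | 62% | 2.25 |
| 0.5 | 4 | 19.9% | 1.40 | 66% | 2.32 |
| 1 | 1.5 | 10.1% | 1.20 | 60% | 2.21 |
| 1 | 2 | 14.3% | 1.29 | 67% | 2.33 |
| 1 | 3 | 19.6% | 1.39 | 73% | 2.45 |
| 1 | 4 | 22.7% | 1.45 | 75% | 2.51 |

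**What a split would show.** In the example with tripling in years 5–7, the pooled interval expects 8.7 events against 2.9 at background. The Poisson probability of 9 or more at background is 0.003. That figure is for all 800 pooled, placebo included. In a cell of 100 to 200 participants (assumed), the expectation is 0.4–0.7 at background and 1.1–2.2 if tripled. Three or more events would then occur with probability only 0.10 to 0.37.

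**The case against.** The strongest reply has five parts.

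- **Timing is recorded.** The listing shows days since last dose for every collected event, and the example expects only about 20 to 26 malignancies, so late cases can be read one by one. This stands. A reader might infer that timing is absent from all output, and it is not. What is missing is the person-time needed to judge whether the late cases are more than expected.
- **Masking depends on onset.** A reader might infer that any late rise would be averaged away. The documents do not support that: they speak of years after exposure and name no year. A rise from year 2 would move the percent clearly.
- **Early events need not dominate.** A reader might picture tumours within months of the last dose filling the percent. Events before 16996 consent are not counted, so with entry at 0.5 to 1 year most of these drop out, and 47% to 75% of person-time falls after year 2.
- **Other analyses may exist.** The supplemental SAP might include time-based summaries. The point can therefore be made only about this SAP.
- **The study is descriptive.** The protocol lists rates and cumulative incidence as measures that may be used, not as required ones, and no testing is planned. True, but a descriptive study still needs a description that can answer its own question.

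**Conclusion.** The point holds for this SAP. No summary of the primary events is split by time since last dose, and the one output that carries event timing has no matching denominator. The planned percents therefore cannot distinguish a late rise from a constant rate, although late effects are the stated reason for the follow-up.

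That conclusion follows from the text and needs no assumption. Its size does. Tripling changes the crude percent by a factor of 1.16 to 1.45 if confined to years 5 to 7, and by 1.95 to 2.51 if it begins at year 2. Both ranges rest on assumed entry times, survival, background rate and follow-up of all 800 to year 7. Breast cancer participants stop at year 5, so true late person-time would be lower to the extent that they are enrolled. It would be wrong to conclude that a late signal is bound to be lost, or that no sponsor analysis anywhere addresses timing. This is an inexpensive improvement worth making.

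**What to change.** In SAP 6.4.2, add two descriptive tables:

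1. New primary malignancies, with leukemia, myelodysplastic syndrome, aplastic anemia and primary bone cancer as rows.
2. Bone fractures.

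Each gives participants with a first 16996-emergent event and person-years at risk by time since last radium-223 or placebo dose, for example under 2, 2 to under 5, and 5 to 7 years. A participant enters at 16996 consent, placed on the time-since-last-dose scale, and leaves at first event, death or last contact. Show the tables by treatment received, pooled within indication, as well as by feeder study. Restrict the 5 to 7 year interval to prostate cancer, because breast cancer follow-up ends at 5 years. Also list the removal of incidence rates and cumulative incidence in SAP 7.2. If the supplemental SAP already contains such tables, a cross-reference and a pooled version would be enough.

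**Cost.** SAP wording and two tables, with no new data and no testing. SAP 5.2.1 already brings in the "date of last radium-223 dichloride or placebo and number of injections received" from the feeder studies; consent, event start, last-known-alive and death dates are already used elsewhere in the plan. The drawback is sparse late cells within a single feeder study and arm, which should be read as description only.

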5.2 Data rules

5.2.1 Integrating Feeder Study Data

Information to be integrated from feeder studies will include (if available): unique participant identifiers (ID), demographic and baseline characteristics (age, height, and weight), intervention randomized to, intervention received, and treatment exposure data, including date of first administration of study drug, date of last radium-223 dichloride or placebo and number of injections received. Only data from eligible feeder studies will be integrated. Data will be merged by feeder study unique subject ID as documented in the 16996 CRF.

5.2.2 Other Data Rules

Participants will be identified in listings by feeder study ID number/16996 participant ID number (concatenated).

Protocol No.: **BAY 88-8223/16996** Page: 9 of 17

5.3 Handling of Dropouts

A participant who discontinues study participation prematurely for any reason is defined as a "drop-out".

Premature discontinuation from study 16996 is defined as discontinuation from study 16996 prior to the end of the applicable long-term-follow-up period from the last date of radium-223 dichloride or placebo treatment in the feeder study (5 years for mBC, 7 years for mCRPC).

The reason for discontinuation for participants who withdraw from study 16996 will be recorded in the electronic case report form (eCRF) and summarized in the analysis. Summaries of premature discontinuation will be provided for SAF-LTF participants.

5.4 Handling of Missing Data

All missing or partial data will be presented in participant data listings as they are recorded in the eCRF.

Missing data will not be imputed for statistical analysis, with the exception of imputation for determining start dates of AEs. See Appendix 8.1 for details.

5.5 Interim Analyses and Data Monitoring

A series of safety analyses will be performed separately for each applicable feeder study, after the last participant from the feeder study completes the applicable long-term follow-up period (7 years after the last dose of radium-223 dichloride or placebo in the feeder study for mCRPC, 5 years for mBC), or prematurely discontinues from 16996 follow-up. These safety analyses are intended to meet Health Authority requirements to evaluate and report the long-term safety of radium-223 dichloride. For all feeder studies but the last, the relevant analysis will occur prior to the overall end of 16966 and hence will constitute an interim analysis. These safety analyses are described in a separate supplemental SAP for Health Authority Reports.

5.6 Validity Review

Validity Review meeting(s) will be conducted prior to final database lock to review participant validity (inclusion of participants in analysis sets), protocol deviations, and data issues of note. The results of validity review meeting(s) will be documented in Validity Review Reports.

6. Statistical Methodology

6.1 Population Characteristics

6.1.1 Participant Disposition

The number and percentage of ENR participants valid for SAF-LTF will be presented by treatment group, for the overall total of the treatment groups per feeder study, and pooled for the total of Study 16996.

The number of participants enrolled in 16996 (ENR) will be displayed by geographic region, country/region and center for each feeder trial.

Protocol No.: **BAY 88-8223/16996** Page: 10 of 17

Study disposition including the number and percent of participants who enrolled in 16996, who did not complete screening, who entered 16996 long-term follow-up, who discontinued long-term follow-up, and who completed long-term follow-up will be summarized for ENR participants. Reasons for premature withdrawal from long-term follow-up will be provided. Summaries will be provided overall (pooled across feeder studies), by feeder study, and by treatment group within each feeder study.

In addition, summary statistics for the duration of follow-up in SAF-LTF participants, period from 31 days (inclusive) after the last administration of radium-223 dichloride or placebo in the feeder study until the last known alive date, will be presented, and the numbers of participants with at least 6, 12, 18, 24, 36, 48, 60, 72, and 84 months of follow-up will be summarized. This summary of long-term follow-up analysis will combine feeder study and 16996 data.

Summary statistics for the duration of follow-up in study 16996 from the time of signing of the informed consent until the last known alive date in SAF-LTF participants will also be presented. The numbers of participants with at least 6, 12, 18, 24, 36, 48, 60, 72, and 84 months of follow-up will be summarized.

